10.0 ADVERSE EVENT REPORTING

10.1 ADVERSE EVENTS

At each evaluation, the investigator will determine whether any adverse events (AE's) have occurred. For the purpose of this protocol, an adverse event is any undesirable clinical occurrence in a subject that can be attributed to the device or incision closure procedure.

In this study, patients should be encouraged to report AE's spontaneously or in response to general, non-directed questioning (e.g., "How has your health been since the last visit?"). Any time during the study, the patient may volunteer information that resembles an AE. If it is determined that an AE has occurred, the investigator should obtain all the information required to complete the AE Form of the CRF.

The following categories of adverse event severity are to be used:

Mild	Awareness of a sign or symptom that does not interfere with the patient's usual activity or is transient, resolved without treatment and with no sequelae
Moderate	Interferes with the patient's usual activity
Severe	Any fatal or immediately life-threatening clinical experience that requires a subject to be hospitalized, or hospitalization is unduly prolonged because of potential disability or danger to life or because an intervention has been necessitated. This includes events that cause fetal distress, fetal death, congenital abnormality or malignancy or any permanently disabling event.

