10.3 UNANTICIPATED ADVERSE DEVICE EFFECTS

Unanticipated adverse device effects are defined as any serious adverse effect on health or safety or any life-threatening problem or death caused by, or associated with, a device, if that effect, problem, or death was not previously identified in nature, severity or degree of incidence in the investigational plan or application (including a supplementary plan or application), or any other unanticipated serious problem associated with a device that relates to the rights, safety or welfare of subjects.

For the purposes of this study, serious is defined as any significant adverse experience, including those which may be either life-threatening or involve permanent or long term injuries, but excluding injuries that are non-life-threatening and that are temporary and reasonably reversible.

An Investigator must submit to the sponsor and to the responsible Medical Ethics Committee (IRB) any unanticipated adverse device effects occurring during the study as soon as possible, but in no event later than ten (10) working days after the Investigator first learns of the effect.

Contact Name:

[name]
Ohio Pain Clinic
[name]
[name]

Report	Submit To	Description/Constraints
Death	Sponsor	Submit as soon as possible but no later than 10 working days after the Investigator first learns of the event.
	IRB	Submit to IRB per local reporting requirements.
Unanticipated adverse device effect (UADE) ¹	Sponsor	Submit as soon as possible but no later than 10 working days after the Investigator first learns of the event.
	IRB	Submit as soon as possible but no later than 10 working days after the Investigator first learns of the event, or per local reporting requirements, whichever is more conservative.
Other Adverse Device Effects	Sponsor	Submit or report as required per local reporting requirements.
	IRB	Submit or report as required per local IRB reporting requirements.
	Regulatory Body	Submit or report as required per regulations.

Table 11-1: Investigator adverse event reports

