11.2 Safety Analysis

All patients who received treatment will be included in the safety analysis. The proportion of patients with complications will be compared by Fisher's Exact test. The two treatment groups will be compared using t-test for continuous variables and chi square test for category variables. All adverse events will be listed and the frequencies, severity, and relationship to the treatment procedure will be tabulated and compared by treatment groups.

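### The severity grades in 10.1 overlap and mix intensity with outcome, so some events cannot be graded consistently for the 11.2 comparison; the outcome criteria also differ from those for serious in 10.3

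*Combined protocol and SAP*

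**What the plan says.** Section 10.1 gives three severity grades.

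- **Mild**: the patient notices a complaint, and it "does not interfere with the patient's usual activity or is transient, resolved without treatment and with no sequelae". The two conditions are alternatives.
- **Moderate**: "Interferes with the patient's usual activity". Nothing is said about duration, treatment or intensity.
- **Severe**: "Any fatal or immediately life-threatening clinical experience that requires a subject to be hospitalized", or a case where "hospitalization is unduly prolonged because of potential disability or danger to life or because an intervention has been necessitated". It also takes in "fetal distress, fetal death, congenital abnormality or malignancy or any permanently disabling event".

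Section 10.3 defines serious separately, for the purpose of unanticipated adverse device effects (UADEs), as "excluding injuries that are non-life-threatening and that are temporary and reasonably reversible" among its terms. Its reporting table sets a limit of 10 working days for deaths (to the sponsor) and for UADEs (to the sponsor and the IRB). Other adverse device effects are reported as local requirements or regulations demand.

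Section 11.2 uses the grades: "the frequencies, severity, and relationship to the treatment procedure will be tabulated and compared by treatment groups".

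Section 6.0 lists the measures against bias. They are eligibility screening, baseline demographics and training. Neither blinding nor independent review of adverse events is among them.

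**The concern.** A severity table is interpretable only if each event has one grade and the grades rise along one dimension. Here the lower boundary (Mild against Moderate) is not exclusive, and the upper one (Moderate against Severe) changes from interference with activity to outcome.

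What is at stake is the severity comparison between the two pulse width arms. Where two grades are permitted, the choice falls to the person grading, and nothing in the plan keeps that person unaware of the arm. If several sites take part, as the synopsis foresees, each may settle the overlap in its own way.

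A second, smaller matter is that 10.1 and 10.3 both use outcome criteria but not the same ones, so the tables and the reporting rules can treat one event differently.

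**Working it through.** No arithmetic applies: the point depends on no rate, effect size or sample size. The check is to put test events through the definitions as written in 10.1 and 10.3.

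| Test event | Grade under 10.1 | Serious under 10.3? |
|---|---|---|
| A. Interferes with activity, but is short, settles untreated, leaves no sequelae; not life-threatening | Mild and Moderate | No |
| B. Very intense, needs treatment, temporary and reversible; none of the listed outcomes | Moderate at most | No |
| C. Hospital stay prolonged because an intervention was needed; not life-threatening, fully reversible | Severe | No |
| D. First admission for an event that is reversible and not life-threatening | Not Severe on a literal reading | No |
| E. Permanently disabling, no hospitalization | Severe | Yes |

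**Step 1, Mild against Moderate.** Event A satisfies the second alternative in Mild, "or is transient, resolved without treatment and with no sequelae", and also satisfies Moderate. An event that does not interfere with activity is already Mild under the first alternative. The second alternative therefore adds to Mild only events that do interfere, and those are exactly the events that Moderate covers. The clause either creates the overlap or does nothing. No tie-break is stated, such as taking the higher grade. Such events are plausible: 10.2 lists unintended and increased stimulation among the anticipated events.

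**Step 2, Moderate against Severe.** Severe contains no intensity criterion. Event B stops at Moderate, however incapacitating it is. Event E shows the limit of this statement: permanent disability is Severe without any hospital stay.

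**Step 3, 10.1 against 10.3.** The opening words of Severe do not conflict with 10.3, because death and immediate threat to life are not excluded there. The difference lies in the clause on prolonged stay. Its danger-to-life limb is also compatible with 10.3. Its intervention limb is not, as event C shows. Nor is its potential-disability limb, where the disability does not come about and the injury proves temporary.

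**Step 4, consequence for reporting.** A UADE must be serious (or fatal or life-threatening) and not previously identified. If event C is an unanticipated device effect, it fails the first condition. It then falls in the row for other adverse device effects, which has no 10-working-day limit.

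**Step 5, use in the analysis.** Section 11.2 tabulates severity and compares it by treatment group, so steps 1 and 2 reach a planned comparison. Two other safety items do not use the grades: the endpoint in 5.2 (rate of device-related or procedure-related events) and the Fisher's exact test on the proportion with complications.

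**The case against.** The strongest reply is that the consequences are small. The safety endpoint and the one test tied to complications ignore the grades, severity is a supporting table, and nothing shows that grading would differ by arm. This stands, and it limits the point to a planned secondary comparison.

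It can also be said that Mild opens with mere awareness of a sign or symptom, so an event that stops normal activity would hardly be called Mild. Many clinicians would read it so. But the text offers brevity and spontaneous resolution as an alternative to non-interference, and a patient whose activity is interrupted is also aware of the symptom. The overlap remains.

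A third reply is that being Severe without being serious is no contradiction in itself. That is right, and it would be routine once the two concepts are kept apart. The complaint is narrower: 10.1 uses outcome criteria, and they differ from those in 10.3.

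A reader might infer more: that hospitalizations escape expedited reporting because of the severity grades. The documents do not support this. No reporting duty in 10.3 refers to the 10.1 grades. Effects that are not UADEs still go to the sponsor, the IRB and the regulator under local requirements or regulations. Only an unanticipated device effect can lose the fixed limit through the definition of serious. Implant-site infection would be a poor illustration, because 10.2 lists it as anticipated and it would normally be outside the UADE route on any definition of serious.

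**Conclusion.** The point holds as a defect of definition. Mild and Moderate are not mutually exclusive, Severe measures outcome rather than intensity, and the affected events cannot be graded consistently in a comparison that 11.2 plans. Separately, the outcome criteria in 10.1 and 10.3 differ for prolonged stays that are not life-threatening and are reversible. For an unanticipated device effect, that costs the protocol's own 10-working-day limit and no more.

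The size cannot be given. The documents state no adverse event rates, so neither the number of ambiguous events nor any shift between arms can be estimated. A reader might infer that events are misgraded in a known direction, or that every incapacitating event treated outside hospital is graded too low. The first needs data that the plan does not give; the second is contradicted by the permanent-disability criterion.

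The conclusion assumes a literal reading of 10.1 and 10.3. The draft case report forms are in an appendix that is not part of the supplied text, so grading guidance or a seriousness field on the adverse event form cannot be ruled out. The primary endpoint is unaffected. The change should be made before enrollment, since ambiguous grades may not be recoverable afterwards.

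**What to change.** 1. In 10.1, make the three grades mutually exclusive and base them only on intensity or interference with activity. Removing the transient-event alternative from Mild makes Mild and Moderate exclusive. Severe then needs a criterion on the same dimension.
2. Move the outcome criteria now under Severe (death, threat to life, hospitalization or its prolongation, intervention, fetal events, congenital abnormality, malignancy, permanent disability) to a separate yes/no seriousness field, if the adverse event form does not already have one.
3. Reconcile that field with the definition of serious and the reporting table in 10.3, so that an event has the same status in the tables and in reporting. The sponsor must decide which criteria apply. The abbreviation list includes serious adverse device effects but the reporting table has no row for them, so aligning the word serious would not by itself set a deadline for anticipated effects.
4. In 11.2, tabulate severity and seriousness separately by treatment group.

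The cost is wording in 10.1, 10.3 and 11.2 and possibly one more field on the adverse event form. The small downside is that more events may be recorded as serious.

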10.2 ANTICIPATED ADVERSE DEVICE EFFECTS

The following ANTICIPATED EVENTS have been identified as possible complications of implanting neurostimulator leads.

- Infection at implant site
- Pain at implant site
- Bleeding
- Bruising
- Device failure
 - Unintended stimulation
 - Increased stimulation
 - Decreased stimulation
 - Lead breakage/migration
 - Battery depletion
 - Erosion of device
 - General device failure

10.3 UNANTICIPATED ADVERSE DEVICE EFFECTS

Unanticipated adverse device effects are defined as any serious adverse effect on health or safety or any life-threatening problem or death caused by, or associated with, a device, if that effect, problem, or death was not previously identified in nature, severity or degree of incidence in the investigational plan or application (including a supplementary plan or application), or any other unanticipated serious problem associated with a device that relates to the rights, safety or welfare of subjects.

For the purposes of this study, serious is defined as any significant adverse experience, including those which may be either life-threatening or involve permanent or long term injuries, but excluding injuries that are non-life-threatening and that are temporary and reasonably reversible.

An Investigator must submit to the sponsor and to the responsible Medical Ethics Committee (IRB) any unanticipated adverse device effects occurring during the study as soon as possible, but in no event later than ten (10) working days after the Investigator first learns of the effect.

Contact Name:

[name]
Ohio Pain Clinic
[name]
[name]

Report	Submit To	Description/Constraints
Death	Sponsor	Submit as soon as possible but no later than 10 working days after the Investigator first learns of the event.
	IRB	Submit to IRB per local reporting requirements.
Unanticipated adverse device effect (UADE) ¹	Sponsor	Submit as soon as possible but no later than 10 working days after the Investigator first learns of the event.
	IRB	Submit as soon as possible but no later than 10 working days after the Investigator first learns of the event, or per local reporting requirements, whichever is more conservative.
Other Adverse Device Effects	Sponsor	Submit or report as required per local reporting requirements.
	IRB	Submit or report as required per local IRB reporting requirements.
	Regulatory Body	Submit or report as required per regulations.

Table 11-1: Investigator adverse event reports

11.0 STATISTICS

11.1 Study Population

All patients who received treatment will be included in an intent-to-treat (ITT) analysis. A per protocol analysis will also be conducted if there are protocol violators.

11.2 Safety Analysis

All patients who received treatment will be included in the safety analysis. The proportion of patients with complications will be compared by Fisher's Exact test. The two treatment groups will be compared using t-test for continuous variables and chi square test for category variables. All adverse events will be listed and the frequencies, severity, and relationship to the treatment procedure will be tabulated and compared by treatment groups.

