Multi-Center Evaluation of Clinical Outcomes of Pulse Widths <500 μ sec and >1000 μ sec During a Temporary Spinal Cord Stimulation Trial

Title: Multi-Center Evaluation of Clinical Outcomes of Pulse Widths <500 μ sec and >1000 μ sec During a Temporary Spinal Cord Stimulation Trial

Protocol Number: TBD

Device: Nuvectra® Algovita® Spinal Cord Stimulation System

Sponsor: The Ohio Pain Clinic
[name]
[name]

Sponsor Contact: [name]
[name]
[name]
[contact]

Study Sites: TBD

Medical Monitor: [name]
Ohio Pain Clinic
[name]
[name]

Date of Protocol: TBD

Confidentiality Statement

The confidential information in this document is provided to you as an investigator or consultant for review by you, your staff, and the applicable Institutional Review Board. Your acceptance of this document constitutes agreement that you will not disclose the information contained herein to others without written authorization from .

Protocol Synopsis

Sponsor Contact Information Ohio Pain Clinic
[name]
[name]
[name]

Study Purpose The purpose of this study is to evaluate the effect of pulse widths <500 μ sec and >1000 μ sec on clinical outcomes during a temporary SCS trial.

Study Design and Scope The proposed study is a prospective, multi-center, two-arm, randomized, crossover design to be conducted at up to 10 sites. The study will enroll up to 100 subjects in order to include up to 10 subjects in the study per site. Subjects selected to participate in the trial have back and/or leg pain, have been evaluated as a candidate for SCS and have agreed to undergo a temporary SCS trial using the Algovita® system with percutaneous leads. Each subject will be followed during the trial period of approximately 7+-2 days. The study will end when the last subject has completed the trial period and exited. The expected enrollment period for this study is approximately six months. After exit from the clinical study, subjects will continue to be followed by their physician per usual care. All device and procedure-related AEs will be collected and reported per the study protocol.

Primary Effectiveness Objective Compare the change in the patient defined pain coverage map from baseline to the end of the 7+-2 day trial.

Secondary Effectiveness Objectives Secondary measures of therapy effectiveness will include:

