- Compare the change from baseline of pain scores between the two study arms. Pain scores are obtained using the Numeric Rating Score (NRS) administered at baseline and after completion of each arm of the study.
- Paresthesia distribution: At end of each arm, subjects will be asked to complete a diagram that shows distribution of paresthesia.
- At the end of the trial period, subjects will be asked to select their favorite program.
- At the end of the trial period, subjects will be asked to rate the quality of the pain relief achieved during the trial (from either arm) using the following scale; *Excellent, Very Good, Good, Fair or Poor*.
- At the end of the trial period, subjects will be asked to rate their overall satisfaction with the pain relief achieved during the trial (from either arm) using the following scale: *Very Satisfied, Satisfied, Neither Satisfied nor Unsatisfied, Unsatisfied, or Very Unsatisfied*.

Secondary Safety Objectives Secondary measures of therapy safety will include:

- Rate of device-related and/or procedure-related AEs from the Trial procedure through study completion.

Study Procedures After the subject has consented to the study, he or she will be enrolled in the clinical study and undergo a baseline evaluation. The patient will then be randomly assigned to arm one (pulse width <500 μ sec) or arm two (pulse width >1000 μ sec) and undergo an Algovita® trial procedures. Following the trial procedure, the subject's EPG will be set to the appropriate pulse width, based on the arm assigned, and then programmed to achieve optimal pain relief. For the next three days, the subject will evaluate pain relief generated by the 1st assigned program (arms).

After 3 days, the patient will visit the Ohio Pain Clinic for data collection and then reprogramming of the EPG for the next arm. For the next three days, the subject will evaluate the SCS therapy generated by the 2nd assigned program and then return to the clinic for data collection, removal of the leads and exit from the study. After the subject is exited from the study, he or she will be followed by the Ohio Pain Clinic per usual care. The data collection requirements are listed below.

Enrollment:

- Informed consent signed
- Confirmation of study eligibility

Baseline evaluation:

- Record pain ratings and pain map
- Relevant medical history
- Physical examination
- Brief Pain Inventory
- Demographics

After the lead implantation:

- Implant procedure

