5.1 PRIMARY EFFECTIVENESS ENDPOINT

The primary effectiveness endpoint is defined as the percent reduction from baseline in targeted patient generated pain map coverage between the two arms.

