5.2 SECONDARY ENDPOINTS

Endpoints for secondary measures of therapy effectiveness:

- To evaluate the effect of conventional pulse widths and pulse widths $>1000\mu\text{sec}$ clinical outcomes during temporary trial as measured by the percent reduction in targeted pain compared to baseline using the NRS at the end of the trial period.
- Comparison of paresthesia overlap of pain between each arm as evaluated by the reviewer to determine which arm had superior pain overlap (coverage)
- Patient *preference* for pulse widths $>1000\mu\text{sec}$ or $<500\mu\text{S}$
- Patient *satisfaction* for pulse widths $>1000\mu\text{sec}$ or $<500\mu\text{S}$
- Number of patients who achieved $\geq 50\%$ pain relief during the trial (from either arm)
- Rate of device-related and/or procedure-related AEs from Trial Lead implant through study completion.

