9.1.6 STUDY EXIT

A Study Exit CRF must be completed for any subject who signed an informed consent form, as they are considered enrolled in the study. Data to be collected at this visit includes:

- Record paresthesia and pain map for current arm
- Record pain rating for current arm
- Record program preference

- Record satisfaction and pain relief from each program
- Study exit date and reason for study exit

Additional data that will be collected as they occur include:

- Device or procedure related AEs
- Technical Observations/Device Deficiencies
- Surgical Interventions

The following scenarios may lead to study exit and will require completion of a Study Exit CRF.

- Inclusion/exclusion criteria not met
- Subject ineligibility for implant, in the opinion of the study physician
- SCS lead removal without re-implantation
- Implant attempted, however no SCS was implanted
- Voluntary withdrawal by subject
- Investigator chooses to withdraw a subject
- Failure to maintain adequate study compliance
- Subject Death

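### The crossover's primary pain-map endpoint has no stated analysis, and the only tests named, under Safety Analysis, are worded for independent groups

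*Combined protocol and SAP*

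**What the plan says.** The Protocol Synopsis (Study Procedures) and section 4.0 describe a randomized two-arm crossover. Each subject is assessed under one pulse width, reprogrammed after about three days, and assessed under the other.

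Section 5.1 sets the primary endpoint: "The primary effectiveness endpoint is defined as the percent reduction from baseline in targeted patient generated pain map coverage between the two arms". It names no test or model.

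Section 11.0, Statistics, has two subsections, and the table of contents lists the same two:

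- Section 11.1 covers populations only: "All patients who received treatment will be included in an intent-to-treat (ITT) analysis", with a per-protocol analysis if there are violators.
- Section 11.2, headed Safety Analysis, is the only text that names tests: "The proportion of patients with complications will be compared by Fisher's Exact test" and "The two treatment groups will be compared using t-test for continuous variables and chi square test for category variables".

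The text is also divided on which data enter the comparison:

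- **Pain map.** Section 5.1 compares the arms. The Synopsis objective reads "Compare the change in the patient defined pain coverage map from baseline to the end of the 7+-2 day trial", while the study-exit list (section 9.1.6) says "Record paresthesia and pain map for current arm", which at exit is the second program.
- **NRS.** The Synopsis has it "administered at baseline and after completion of each arm of the study". Section 5.2 has "percent reduction in targeted pain compared to baseline using the NRS at the end of the trial period", and section 2.2, item 1, says the same.

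Section 4.0 aims for at least 50 subjects and section 8.3 caps the study at 100. No significance level, power, effect size, SD, within-subject correlation or allocation ratio is given.

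**The concern.** In a crossover the treatment effect is estimated from differences within subjects. An analysis that ignores the pairing uses the wrong standard error, and one that ignores period relies on the two orders being balanced. The protocol states neither for its primary endpoint. The tests it does name are described as comparing two groups of patients, whereas the two pulse widths are given to the same patients.

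Two things are at stake. If section 11.2 is carried over to effectiveness as worded, the trial gives up the precision that the crossover was chosen to provide. If it is not carried over, the primary comparison has no prespecified method, and the choice stays open until the data are in hand.

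**Working it through.** **1. What the text settles.** The plan has no statistical figure to reproduce, because 100 is a cap without a derivation. The omission is established by reading: section 5.1 has no test, section 11.1 has populations only, and section 11.2 has tests under a safety heading. In section 11.2 the t-test is unqualified, so it could be paired. Chi-square and Fisher's exact, applied to two groups, are independent-sample tests.

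**2. Effect of ignoring the pairing.** Taken from the protocol: N = 50 (section 4.0) and N = 100 (section 8.3). Assumed, because not given: normal outcomes with equal variances, a true difference of 0.4 SD, two-sided 5%, equal orders, no carry-over, and within-subject correlation r from 0 to 0.7. In SD units:

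- Standard error used by an unpaired test: √(2/N) = √(2/50) = 0.200, whatever r is.
- True standard error of the difference: √(2(1−r)/N). At r = 0.5 this is √(1/50) = 0.141.
- Actual type I error of the unpaired test: 2[1 − Φ(1.96/√(1−r))]. At r = 0.5 this is 2[1 − Φ(2.77)] = 0.0056.
- Smallest difference detectable with 80% power at N = 50: (1.96 + 0.84) × 0.200 = 0.56 unpaired, and (1.96 + 0.84) × 0.141 = 0.40 within subject at r = 0.5.

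The power figures below come from simulation. The within-subject figures at N = 50 agree with the noncentral t distribution.

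| r | 0 | 0.3 | 0.5 | 0.7 |
|---|---|---|---|---|
| N = 50, power, unpaired | 51% | 51% | 51% | 52% |
| N = 50, power, within-subject | 50% | 65% | 79% | 95% |
| N = 50, actual type I error, unpaired | 5% | 2% | 0.6% | <0.1% |
| N = 50, detectable difference, within-subject (unpaired 0.56 SD) | 0.56 | 0.47 | 0.40 | 0.31 |
| N = 100, power, unpaired | 80% | 85% | 89% | 94% |
| N = 100, power, within-subject | 80% | 92% | 98% | 99.9% |

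**3. Effect of pairing but omitting period.** At N = 50 and r = 0.5, with an assumed period difference of 0.3 or 0.5 SD:

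- Orders 25:25: no bias. Power falls from 79% to about 76% or 72%.
- Orders 30:20: bias = period difference × (30 − 20)/50, which is 0.3 × 0.2 = 0.06 SD or 0.5 × 0.2 = 0.10 SD. Type I error is 6.0% or 7.1%. The period-adjusted test stays unbiased at about 5%.
- Simple 1:1 randomization, averaged over the splits it produces: mean bias zero, type I error 5.1% or 5.2%.

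**4. The separate end-of-trial wording.** Suppose end of trial were taken to mean comparing second-period results between the two orders. The standard error at 25:25 is √(2/25) = 0.283 SD, and power for 0.4 SD is about 28% at N = 50 (51% at N = 100). With no true effect, taking the smaller p-value of this test and the period-adjusted crossover test gives 8.4% / 8.9% / 9.0% / 9.3% false positives at r = 0 / 0.3 / 0.5 / 0.7. By contrast, taking the smallest p-value of four tests that all use both periods (unpaired, paired, period-adjusted, Wilcoxon signed-rank) gives only 5.9% to 6.4%.

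**The case against.** The best defence is that section 11.2 concerns safety, so its tests were never meant for the pain map, and that a competent statistician would pair the data anyway. The first half is fair: nothing in the protocol says that section 11.2 governs the primary endpoint. But then the primary endpoint has no analysis at all. As to the second half, nothing in the text requires pairing, and pairing alone settles neither period nor which maps are used.

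Several stronger readings are tempting, and the documents do not support them.

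- *The named tests inflate false positives.* They do not. Under positive correlation the unpaired test is conservative, and its cost is power.
- *The plan commits to an unpaired t-test.* The word unpaired does not appear, and a paired t-test is not excluded.
- *The missing test nearly doubles the false-positive rate.* The 8% to 9% comes from the end-of-trial wording, and only if that wording is read as a second-period comparison. No section describes such an analysis, and the phrase can equally be read as a time frame.
- *Omitting period biases the result.* It does so only when the orders are unequal in size, and nothing in the protocol points to unequal allocation.
- *Fisher's exact test is invalid here.* For a per-patient complication rate compared between the two randomized orders it is valid. It does not suit a comparison of pulse widths within the same patients. The text does not say which comparison is meant.

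**Conclusion.** The point holds and should be fixed before outcome data are examined. The primary endpoint of a randomized crossover has no stated analysis, and the only tests named are worded for independent groups.

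If those tests were applied to the two pulse widths, the loss at 50 subjects would run from nothing at r = 0 to 52% power against 95% at r = 0.7, always in the conservative direction. These sizes rest on the assumptions in the working, none of which the protocol supplies. The 0.4 SD effect in particular is illustrative, and normality may not suit a percent reduction. The omission itself rests on no assumption. Leaving period out is a minor matter if the orders are equal in size. The end-of-trial wording is a related but distinct conflict about which data are compared.

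**What to change.** **Effectiveness analysis.** Add to section 11 that percent reduction in the pain map, using the maps from both programs, is compared within subject with period adjustment. Either a period-adjusted crossover t-test would do, or a mixed model with treatment, period and sequence as fixed effects and subject as random effect. The mixed model also keeps subjects who contribute only one period. Specify the same for the NRS.

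**Wording.** Align the end-of-trial phrasing in the Synopsis primary objective, section 2.2 item 1 and the first endpoint of section 5.2 with the per-arm comparison.

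**Section 11.2.** Define treatment groups. Where outcomes are compared by pulse width, use paired methods that suit the scale: McNemar or an order-adjusted binary method for per-arm binary outcomes, and a paired ordinal method for ratings recorded per program. The responder count (at least 50% relief) is defined across either arm, so as written it is not a per-arm outcome. Keep Fisher's exact only for comparisons between the randomized orders.

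**Adverse events.** In the analysis, attribute each event to the program running at onset, and do not attribute lead-procedure events to a pulse width.

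**Cost.** Rewording of section 11 and three objective or endpoint sentences, plus recording adverse-event onset relative to reprogramming. Maps are already collected under each program, so no extra patients or visits are needed.
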